^e After initiation of methadone treatment and prior to discharge during the weaning phase of narcotic treatment

^f Home visit or phone interview

Principal Investigator: [name], MPH

Application Number: IRB00107690

Comparison Group:

Study Intervention	Enrollment	While inpatient	6 – 8 weeks of age
Informed Consent	X		
The Postpartum Bonding Questionnaire (PBQ)		X ^a	X ^b
Edinburgh Postnatal Depression Scale (EPDS)		X ^a	X ^b

^a After initiation of standard of care narcotics for treatment of NAS and prior to discharge during the weaning phase of narcotic treatment

^b Administered either through a home visit by Kids Home Care or via a phone interview conducted by a study team member

Routine (usual) care for infants born to mothers with a history of opiate use: All infants have routine scoring with the modified Finnegan scoring tool approximately every 3 to 4 hours per standard of care for signs of NAS. Infants will be managed with comfort, non-pharmacological measures. Initiation of medical treatment will take place when 2 consecutive Finnegan scores are > 8. Escalation of treatment and weaning will follow set protocols. Vital signs, blood pressures and cardiorespiratory monitoring follow the NICU standard of practice. Outpatient neurodevelopmental follow-up is offered at 1 and 2 years of age.

Comparison Group:

The comparison group of mother/baby dyads will receive standard of care treatment. The study interventions in this group are limited to the bonding and depression assessments. All other data required for analysis of the study aims can be abstracted from the baby's medical record as it is part of standard clinical care.

Methadone Treatment group:

A. Infant participants will receive the following services not part of the standard of care at JHACH:

- a) Initiation of the commercially available methadone treatment instead of morphine as pharmacologic treatment (see methadone treatment below);
- b) Maternal education on recognizing signs and symptoms of withdrawal as well as understanding and performing adequate Finnegan scoring. Specifically, mothers will be taught how to demonstrate tone and tremors on Physical exam.
- c) Provision of close psychological and emotional support to mothers

Principal Investigator: [name], MPH

Application Number: IRB00107690

- d) Facilitation of prolonged maternal physical presence at her infant's bedside

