Safe Dispensing of Study Drug: The investigational research pharmacy at JHACH is directing the dosing and distribution of the methadone through a locked and password coded drug-dispensing system (as is routine for opiates). Home use of methadone is regulated by the FDA and the State of Florida.

Adverse Events

An adverse event is defined as any untoward medical occurrence associated with the use of a drug in humans, whether or not considered drug-related.

- Adverse events will only be collected on those participants who receive demonstration study drug
- This study will only capture adverse events (AE) that meet at least ONE of the following criteria:

Principal Investigator: [name], MPH

Application Number: IRB00107690

- The AE is at least possibly related to the demonstration study drug AND is unexpected in nature or severity
- The AE is a serious adverse event (SAE) as defined below*.
- The AE is one of the following adverse events of interest:
 - Respiratory depressions (respirations < 20/min by auscultation)
 - Bronchospasm
 - Angioneurotic edema
 - Anaphylactic shock
 - Need for respiratory support
 - Cardiovascular compromise requiring fluid replacement

The following will be collected and/or accessed for each adverse event:

- AE Start date and stop date
- AE Severity: mild, moderate, or severe
- AE relatedness to study drug: unrelated, possibly related, probably related, or definitely related
- AE expectedness: An adverse event is considered “unexpected” if it is not listed in the package insert or is not listed at the specificity or severity that has been observed.
- AE seriousness: An adverse event is considered a Serious Adverse Event (SAE)* if it results in one of the following outcomes:
 - Death
 - A life-threatening adverse event (an adverse event is considered “life-threatening” if its occurrence places the patient or subject at immediate risk of death. It does not include an adverse event that, had it occurred in a more severe form, might have caused death)
 - Inpatient hospitalization or prolongation of existing hospitalization
 - A persistent or significant incapacity or substantial disruption of the ability to conduct normal life functions

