 - A congenital anomaly/birth defectOr another important medical event that may not have resulted in death, been life-threatening, or required hospitalization, but nonetheless still considered serious when, based upon appropriate medical judgment, the event jeopardized the patient or subject and may require medical or surgical intervention to prevent one of the above outcomes listed in this SAE definition

Adverse Event Reporting Requirements:

Any safety-related event meeting the JHM IRB’s definition of an unanticipated problem will be appropriately documented, reported, and followed per institutional policies.

c. Plan for reporting unanticipated problems or study deviations:

All adverse events that meet the criteria of an Unanticipated Problem Involving Risks to Subjects or Others (UPIRSO) will be reported by the PI or designee to the JHM IRB per JHM IRB policy. A master cumulative Protocol Deviation log will be used by the PI and study team to log all study deviations and will be reported to the IRB per institutional policies.

Principal Investigator: [name], MPH

Application Number: IRB00107690

d. Data Safety and Monitoring Plan:

Data safety and monitoring will be done by a JHACH pediatrician ([name]) who is experienced in the care of sick newborns. He is independent from the investigative team. His primary focus will be on drug related toxicity and protocol adherence. [name] will review the protocol at staged points as follows:

- 1) Prior to the start of the trial
- 2) After accrual of the first 50% (n=13) of infants treatment in the methadone treatment group
- 3) After accrual of the second 50% (n=12) of infants treatment in the methadone treatment group
- 4) At the completion of the trial

Stopping for harm will be done at the judgment of [name], as the data safety monitor, taking into account the seriousness and estimated excess risk of any observed adverse effects and the strength of the statistical evidence for the adverse effects.

Along with [name], everybody on the research team will be adherent to strict safety parameters and will be monitoring for moderate and severe cardiorespiratory events that require positive pressure ventilation and/or fluid resuscitation as intervention.

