Stopping procedures were computed using the sequential probability ratio test (SPRT) with alpha set at .05 and power at 80%. Adverse events were examined based on three categories of (1) severe, (2) moderate requiring oxygen or room air flow, and (3) moderate requiring tactile stimulation. Using baseline rates of 8%, 13%, and 8%, accordingly for categories 1 through 3 above, and excessive rates of 13%, 25%, and 17%, accordingly, stopping procedures were calculated as follows:

- Severe AE
 - Moderate AE (oxygen/flow)
 - Moderate AE (tactile stimulation)
- 1) Using baseline rate of 8% and excessive rate of 13%, the first 5 events would not stop the trial. But the following would require a stop:
 - If 6 of the first 8 patients have a severe adverse event
 - If 7 of the first 17 patients have a severe adverse event
 - If 8 of the first 27 patients (goes out of our sample size) have a severe adverse event
 - 2) Using baseline rate of 13% and excessive rate of 25%, the first 4 events would not stop the trial. But the following would require a stop:
 - If 5 of the first 8 patients have a moderate adverse event requiring oxygen/flow
 - If 6 of the first 13 patients have a moderate adverse event requiring oxygen/flow

Principal Investigator: [name], MPH

Application Number: IRB00107690

- If 7 of the first 18 patients have a moderate adverse event requiring oxygen/flow
- If 8 of the first 24 patients have a moderate adverse event requiring oxygen/flow

3) Using baseline rate of 8% and excessive rate of 17%, the first 3 events would not stop the trial. But the following would require a stop:

- If 4 of the first 6 patients have a moderate adverse event requiring tactile stimulation.
- If 5 of the first 14 patients have a moderate adverse event requiring tactile stimulation.
- If 6 of the first 22 patients have a moderate adverse event requiring tactile stimulation
- If 7 of the first 30 patients (goes out of our sample size) have a moderate adverse event requiring tactile stimulation.

For this trial we define “unsafe” if the use of methadone is associated with frequency of moderate or adverse cardiorespiratory events that requires an intervention that exceeds a specified thresholds outlined above that is sufficient to stop the trial. Thus unsafe and stopping parameters should be the same in this small trial.

e. **Legal risks such as the risks that would be associated with breach of confidentiality:**

N/A

f. **Financial risks to the participants:**

N/A

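### Adverse events are collected only in methadone infants, so excess risk can be judged only against three baseline rates with no stated source, and no planned data can check those rates

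*Combined protocol and SAP*

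**What the plan says.** Section 7.b, under Adverse Events, limits collection to one group: "Adverse events will only be collected on those participants who receive demonstration study drug". Within that group it captures unexpected events that are at least possibly drug-related, all serious adverse events, and a short list of events of interest, mostly respiratory, cardiovascular and allergic.

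Section 7.d leaves stopping for harm to an independent pediatrician, "taking into account the seriousness and estimated excess risk of any observed adverse effects" and the strength of the statistical evidence. It then gives sequential probability ratio test (SPRT) limits at alpha 0.05 and 80% power: "Using baseline rates of 8%, 13%, and 8%, accordingly for categories 1 through 3 above", with "excessive rates of 13%, 25%, and 17%, accordingly". The three categories are severe events, moderate events needing oxygen or flow, and moderate events needing tactile stimulation. Section 7.d adds that the trial's definition of unsafe should coincide with these limits. No source, population or period is given for the baseline rates.

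For the comparison group, Study Procedures limits study interventions to the bonding and depression questionnaires, and says of the rest: "All other data required for analysis of the study aims can be abstracted from" the medical record. Section 6.c compares 30-day readmission between the groups.

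**The concern.** An excess needs a reference. Section 3 lists respiratory distress among the signs of neonatal abstinence syndrome, so a count in methadone infants alone mixes disease with drug. Section 7.a frames methadone's respiratory risk relative to oral morphine, the unit's routine treatment. Yet the infants who receive that treatment within the trial have no adverse events recorded.

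If the true background in these infants is above the stated baseline, the rule can stop a trial in which methadone adds nothing. If it is below, a real excess can pass as baseline. Other captured events, such as bronchospasm, anaphylactic shock or serious events outside the three categories, have no stated reference rate. The report also could not set adverse event rates side by side.

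**Working it through.** **Inputs (Sections 7.d and 6.c).** Baseline rates p0 = 8%, 13%, 8%; excessive rates p1 = 13%, 25%, 17%; alpha 0.05; power 80%; 25 infants per group. Stated oxygen/flow limits: 5 of the first 8, 6 of 13, 7 of 18, 8 of 24.

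**1. Reproduce the limits.** In a one-sample Wald SPRT the upper boundary is ln(0.80/0.05) = 2.773. With r events, stop if they occur within

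n = r + [r·ln(p1/p0) − 2.773] / [−ln((1−p1)/(1−p0))]

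For oxygen/flow, ln(0.25/0.13) = 0.654 and −ln(0.75/0.87) = 0.148. This gives n = 8.35, 13.75, 19.16 and 24.57 for r = 5, 6, 7 and 8; rounded down, 8, 13, 19 and 24. Across the three categories, 8 of the 11 stated limits match exactly and 3 differ by one patient. The limits therefore follow from the fixed rates alone, and no comparison-group data enter them.

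**2. Chance of stopping when methadone adds nothing.** Let f_n(k) be the probability of k events after n infants without having stopped:

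f_n(k) = (1−p)·f_{n−1}(k) + p·f_{n−1}(k−1)

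For oxygen/flow, stop at 5 events up to infant 8, 6 up to infant 13, 7 up to infant 18 and 8 up to infant 24. Each rule is taken alone, applied after every infant, to n = 25. With no excess, the methadone rate p equals the background rate.

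| Background rate | Oxygen/flow rule stops | Status of the rate |
|---|---|---|
| 13% | 1.2% | stated baseline |
| 20% | 10.5% | assumed |
| 25% | 26% | assumed (equals the plan's excessive rate) |

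The tactile rule behaves alike: 0.9% at the stated 8%, and 6.9% at an assumed 13%.

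The stopping probability depends only on the rate in methadone infants. The background decides what the stop means: at 25%, a stop signals harm if the background is 13% and is a false alarm if it is 25%. The planned data cannot tell these apart.

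**3. What comparison-group data would add.** At the plan's own rates with 25 per group, the 95% half-width of the risk difference is 1.96·√[p0(1−p0)/25 + p1(1−p1)/25]. For oxygen/flow this is 1.96·√(0.00452 + 0.00750) = 0.215.

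| Category | Excess in the plan (points) | Half-width (points) | Two-sided Fisher exact power |
|---|---|---|---|
| Severe | 5 | ±17 | 2% |
| Oxygen/flow | 12 | ±21 | 11% |
| Tactile | 9 | ±18 | 7% |

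Three events in 25 comparison infants would give 12%, with a Clopper-Pearson 95% interval of 2.5% to 31%. That would expose a badly wrong baseline but could not settle a moderate error.

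**The case against.** A reader might infer that the monitor cannot estimate an excess risk at all. The documents do not support that. Section 7.d supplies reference rates for three categories, its limits need only methadone counts, and it equates unsafe with crossing them. The excess is estimable; what is missing is support for the reference, and any reference for other events.

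The other side also has a fair case against the remedy:

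- The comparison infants are not a clean background. Section 4 excludes maternal drug screens positive for non-opiate drugs of abuse only in the methadone group, and only that group's mothers must be compliant with their program on a stable dose. Standard care is morphine with clonidine adjunct.
- The comparison has little power, and the interval for 3 of 25 covers every baseline and excessive rate in the plan.
- Nothing ties comparison accrual to methadone accrual, so data may be sparse at the first review.
- Only inpatient events can be compared; the home treatment period has no comparator.
- Chart abstraction is planned for the study aims, which do not include adverse events, and the documents do not say that tactile stimulation is routinely charted.

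All of this stands. It limits the comparison to descriptive context. It does not supply a source for the baselines, and it does not show that a rough concurrent figure is worse than none. The 20% and 25% backgrounds are indeed assumptions; the documents point to neither.

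**Conclusion.** The point holds as a gap in the reference for harm, not as a failure of the stopping rule's arithmetic, which reproduces. Excess risk can be judged only against three unsourced rates, and no planned data can check them. The consequence for the oxygen/flow rule is a chance of stopping without any methadone excess of 1.2% at the stated background, rising to 10.5% or 26% if the background were 20% or 25%. These figures assume independent infants, the stated limits checked after each infant, and 25 infants in total.

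Two further inferences should be resisted. The report would not lack every between-group safety comparison, since 30-day readmission is already compared; the gap is in adverse event rates. And comparison-group data would not recalibrate the SPRT limits or change how often they trigger. Their value is as a rough check on the baselines and as context for the monitor's judgment. This is a worthwhile, inexpensive improvement.

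**What to change.** 1. In Section 7.d, state the source, population and period of the 8%, 13% and 8% rates, and say what the excess risk is measured against.
2. In Section 7.b, extend collection to comparison infants by chart abstraction over the inpatient opioid period. Cover the three stopping categories, as far as they are charted, and the listed events of interest. Tactile stimulation is a stopping category but not a listed event of interest, so confirm its capture in both groups.
3. Give the monitor both groups' rates at the scheduled reviews (after 13 and after all 25 methadone infants). Separate methadone inpatient events from home events so that like is set beside like, and show inpatient opioid days because the plan expects length of stay to differ.
4. Report the two groups side by side as descriptive, with exact confidence intervals and no formal test. State that the comparison is non-randomized and confounded, and keep the SPRT limits as the formal rule.

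The cost is a protocol amendment and modest data entry for about 25 infants who are already consented and whose charts are already to be abstracted. Section 7.b describes continuous saturation and cardiorespiratory monitoring as standard for all infants in the unit, so no new procedure is needed. The main risk is over-reading a small, confounded difference, which the descriptive label and the intervals are meant to prevent.

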JHACH admitted and average of 131 NAS infants in recent years who required pharmacological treatment for NAS. Approximately 30% of those mother/infant dyads were residents of PAR. We anticipate to enroll 25 mother/baby dyads into the methadone treatment group and 25 mother/baby dyads into the control group for a total of 100 participants. Both the mother and infant are research participants. Those infant participants are defined as 1) needing methadone or other opiate treatment, 2) transitioning to home care, and 3) successfully weaning off medication.

This number has been extrapolated taken into account the following projections/assumptions: 1) not all mothers staying at PAR will meet criteria for participation, and 2) polydrug use may be discovered at the time of delivery thus excluding from participation, and 3) 20-40% of infants enrolled may need adjunct second line therapy.

b. Blinding, including justification for blinding or not blinding the trial, if applicable.

This is a demonstration study with no blinding of subjects involved.

c. Justification of why participants will not receive routine care or will have current therapy stopped.

All infants will continue to receive routine hospital care. Methadone treatment is approved by the FDA, and endorsed by the AAP for inpatient and outpatient treatment of infants with NAS. While methadone is not used as the standard of care at JHACH NICU for infants with NAS at birth, it is still used for later iatrogenic withdrawal in the NICU and other intensive care units in the hospital.

d. Justification for inclusion of a placebo or non-treatment group. N/A Will need to justify this as a comparison groups has been included

e. Definition of treatment failure or participant removal criteria.

As delineated above, infants will be off-treatment from the demonstration project if 1) they require the addition of a second-line of pharmacological treatment or 2) they require re-admission to the

Principal Investigator: [name], MPH

Application Number: IRB00107690

hospital. Data will still be collected until final hospital discharge for these infants and the maternal assessments of bonding and depression will remain ongoing. .

Other Indications for participant off-study:

- a. Parent withdraws informed consent at any time
 - b. Infant transfers to another hospital.
 - c. Infant experiences an unexpected adverse event deemed related to study intervention

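### The safety stopping rule is described as having 80% power, but within 25 methadone infants its boundaries stop the trial at the plan's own excessive rates only about 1%, 26% and 18% of the time.

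*Combined protocol and SAP*

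**What the plan says.** Section 7.d (Data Safety and Monitoring Plan) states: "Stopping procedures were computed using the sequential probability ratio test (SPRT) with alpha set at .05 and power at 80" percent. It gives baseline rates of 8%, 13% and 8% and excessive rates of 13%, 25% and 17% for severe events, moderate events needing oxygen or flow, and moderate events needing tactile stimulation. The boundaries, written as events / first n patients, are:

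- severe: 6/8, 7/17, 8/27
- oxygen/flow: 5/8, 6/13, 7/18, 8/24
- tactile: 4/6, 5/14, 6/22, 7/30

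Two of these are flagged as lying beyond the sample, for example "If 8 of the first 27 patients (goes out of our sample size) have a severe adverse event". The section defines unsafe as exceeding these thresholds and concludes: "Thus unsafe and stopping parameters should be the same in this small trial".

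The Accrual paragraph fixes the size: "We anticipate to enroll 25 mother/baby dyads into the methadone treatment group". Section 7.d schedules monitor reviews before the start, after 13 infants, "After accrual of the second 50% (n=12) of infants treatment in the methadone treatment group", and at completion. Stopping for harm is left to the independent monitor's judgement.

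On event capture, the Adverse Events part of section 7 says "This study will only capture adverse events (AE) that meet at least ONE of the following criteria" and then lists them. "Need for respiratory support" is on the list; tactile stimulation is not. Section 7.d describes the team as "monitoring for moderate and severe cardiorespiratory events that require positive pressure ventilation and/or fluid resuscitation as intervention".

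**The concern.** A sequential probability ratio test has its nominal error rates only if sampling is allowed to run until a boundary is reached. Here accrual ends at 25. The plan notes that two boundaries fall outside the sample, but it does not say what the cap does to the probability of stopping. The only sensitivity figure a reader is given is 80%.

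This matters because the same thresholds serve as the definition of unsafe, in newborns receiving an opioid partly at home. A reader, or the monitor when weighing the statistical evidence, could take an uncrossed boundary as a result that an unsafe rate would have avoided four times in five.

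Two points of application add to this. The plan does not say when the counts are compared with the boundaries: the first-n-patients wording suggests continuous checking, while the only accrual-based reviews fall at 13 and 25. And the third category counts events that the capture list does not name.

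**Working it through.** **Inputs.** Alpha 0.05, power 0.80, the baseline rates (p0), excessive rates (p1) and boundaries from section 7.d; 25 infants from the Accrual paragraph (13 + 12 = 25 in section 7.d).

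**Step 1: reproduce the plan's boundaries.** Wald's upper limit is ln(0.80/0.05) = ln 16 = 2.773. With d events in n infants, stop when

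d·ln(p1/p0) − (n − d)·ln[(1 − p0)/(1 − p1)] ≥ 2.773,

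which rearranges to d ≥ a + s·n, with a = 2.773/(A + B), s = B/(A + B), A = ln(p1/p0) and B = ln[(1 − p0)/(1 − p1)]. The last n at which d events stop the trial is (d − a)/s.

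| Category | A | B | a | s | Last n from formula | Plan |
|---|---|---|---|---|---|---|
| Severe | 0.4855 | 0.0559 | 5.121 | 0.1032 | 8.51, 18.20, 27.89 | 8, 17, 27 |
| Oxygen/flow | 0.6539 | 0.1484 | 3.456 | 0.1850 | 8.35, 13.75, 19.16, 24.57 | 8, 13, 18, 24 |
| Tactile | 0.7538 | 0.1029 | 3.236 | 0.1202 | 6.36, 14.68, 23.00, 31.32 | 6, 14, 22, 30 |

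After rounding down, every listed boundary agrees to within one patient. The plan's boundaries are therefore the upper line of this test.

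**Step 2: check the nominal properties without a cap.** Run open-ended with both Wald boundaries, the test has alpha 4.2%, 4.0% and 3.8% and power 80.4%, 81.0% and 81.0%. Its expected sample size at the excessive rates is about 142, 41 and 51 infants. With only the upper boundary, as listed, reaching an 80% chance of stopping takes about 297, 84 and 105 infants.

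**Step 3: cap at 25.** Expected events at the excessive rates are 25 × 0.13 = 3.25, 25 × 0.25 = 6.25 and 25 × 0.17 = 4.25. Unless an earlier boundary has been crossed, stopping late in accrual needs 8 severe events, 8 oxygen/flow events by infant 24, or 7 tactile events.

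The exact probability comes from a patient-by-patient recursion on the number of events k:

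f_n(k) = f_{n−1}(k)(1 − p) + f_{n−1}(k − 1)p,

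removing as stopped any path with at least d events at or before the patient number listed for d.

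| Category | P(stop) at baseline | P(stop) at excessive rate | True rate giving 80% stopping | P(stop) at a true 40% |
|---|---|---|---|---|
| Severe | 0.06% | 1.2% | 38% | 85% |
| Oxygen/flow | 1.2% | 25.8% | 39% | 82% |
| Tactile | 0.9% | 18.3% | 32% | 95% |

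A simulation of 400,000 trials per category gave the same excessive-rate figures (1.2%, 25.8%, 18.3%).

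**Step 4: any category.** Assuming independence, at least one boundary is crossed with probability 1 − (1 − 0.0123)(1 − 0.2577)(1 − 0.1829) = 40% at the excessive rates, and 2.1% at the baseline rates.

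**Step 5: other readings, at the excessive rates.**

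| Reading | Severe | Oxygen/flow | Tactile |
|---|---|---|---|
| Boundaries marked out of sample do not apply | 0.4% | 25.8% | 17.1% |
| Listed boundaries checked only at 13 and 25 | 1.1% | 8.0% | 13.5% |
| Wald line checked only at 13 and 25 (8, 9 and 7 events at 25) | 1.1% | 17.4% | 13.5% |
| 32 to 42 infants exposed, Wald line extended | 3–6% | 36–49% | 29–39% |

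The second and third rows differ for oxygen/flow because no listed boundary for that category applies after infant 24. The last row assumes that 25 means infants completing the pathway and that 20–40% need second-line therapy, so that 25/0.8 ≈ 32 to 25/0.6 ≈ 42 are exposed. No reading comes near 80%.

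**The case against.** The sentence on alpha and power can be read as naming design inputs. On that reading it is accurate, since the boundaries follow from those inputs. The plan also shows some awareness of the cap by marking two boundaries as outside its sample. It does not claim that staying under the thresholds shows safety. The monitor may stop on judgement, and infants have continuous cardiorespiratory monitoring while in the NICU.

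Much of the shortfall also comes from the size of the trial. A single one-sided exact test at the end of accrual, with alpha no more than .05 in 25 infants, would need at least 5, 7 and 5 events and have power of about 22%, 44% and 42%. So 80% is out of reach for that test too.

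These points stand. They show that the boundaries were not miscalculated and that the rule is not the only protection. They do not remove the problem: 80% remains the only sensitivity quoted, it is attached to the thresholds that define unsafe, and it does not hold in a trial of 25. Clinical discretion is a real safeguard but does not give the numeric rule its stated power.

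On capture, some tactile-stimulation events would be recorded through another item, such as respirations below 20 per minute. How many would be missed cannot be judged from the documents. Oxygen/flow events are reasonably covered by the respiratory-support item.

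**Conclusion.** The concern holds. The nominal 5% and 80% are properties of an open-ended test that this trial does not run. Within 25 infants, stopping at the excessive rates has probability 1.2%, 25.8% and 18.3%, assuming that the listed boundaries are checked after every infant and that infants are independent with a constant event rate. The rule becomes sensitive only at true rates of roughly 32% to 39%. The false-stop risk is well below nominal (about 2% overall, assuming independent categories), so the error is one of overstated sensitivity. The length-of-stay analysis is not affected. The unstated checking schedule and the missing capture item for the third category are smaller points that need clarifying.

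**What to change.** In section 7.d:

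- Describe alpha .05 and power 80% as inputs to an open-ended sequential test.
- State the stopping probabilities within 25 infants: 0.06%, 1.2% and 0.9% at the baseline rates; 1.2%, 25.8% and 18.3% at the excessive rates.
- State that not crossing a boundary does not establish safety.
- Say how the two boundaries marked out of sample are used, for example whether 8 severe events among 25 infants stop the trial.
- Say when counts are compared with the boundaries. The probabilities above assume checking as events accrue, in addition to the staged monitor reviews; they are lower if checks fall only at 13 and 25.
- Reconcile the adverse event capture list and the team-monitoring sentence with the third category, so that events needing tactile stimulation are recorded.

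The cost is protocol wording and one added item of event capture, with no extra infants and no change to existing boundaries. The stated sensitivity will look much less favourable.

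Recomputing boundaries for a maximum of 25 is optional. It would buy sensitivity at the price of a false-stop probability above the present 2% or so. If it is done, the existing early stops should be kept and the false-stop probabilities reported per category and overall.

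### Section 7.d sets a looser stopping list for severe events than for events needing only tactile stimulation, from the same 8% baseline, and the cited 80% power is out of reach for severe events with 25 infants

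*Combined protocol and SAP*

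**What the plan says.** Section 7.d (Data Safety and Monitoring Plan) describes the method: "Stopping procedures were computed using the sequential probability ratio test (SPRT) with alpha set at .05 and power at 80" per cent. It then prints three lists for the methadone group, which the Accrual text puts at 25 infants.

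- Severe (item 1): "Using baseline rate of 8% and excessive rate of 13%, the first 5 events would not stop the trial". Stops come at 6 of the first 8 and 7 of the first 17. The last line reads "If 8 of the first 27 patients (goes out of our sample size) have a severe adverse event".
- Moderate, oxygen or flow (item 2): baseline 13%, excessive 25%. Stops come at 5 of 8, 6 of 13, 7 of 18 and 8 of 24.
- Moderate, tactile stimulation (item 3): "Using baseline rate of 8% and excessive rate of 17%, the first 3 events would not stop the trial". The first line is "If 4 of the first 6 patients have a moderate adverse event requiring tactile stimulation", followed by 5 of 14, 6 of 22 and 7 of 30, the last marked as outside the sample.

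The section closes by equating the definition of unsafe with these thresholds. It also lets an independent monitor stop for harm by judgment, "taking into account the seriousness and estimated excess risk of any observed adverse effects", with in-trial reviews after the first 13 and the remaining 12 methadone infants. Section 7.c says that unanticipated problems "will be reported by the PI or designee to the JHM IRB per JHM IRB policy".

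**The concern.** Setting a lower excessive rate for severe events (13% against 17%) suggests less tolerance of severe harm. In an SPRT the effect is the reverse: the closer the two rates, the more evidence is needed, so the boundary moves up. From a shared baseline, the graver category ends with the looser list, and the plan gives no reason for this.

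These limits guard newborns on an opioid against cardiorespiratory toxicity. Five severe events in the first 5 infants, or in the first 13, reach no limit. Five tactile events in the first 13 would stop the trial. A reader of the method sentence would also take it that each list has 80% power to detect its excessive rate.

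**Working it through.** **Inputs (all from section 7.d and the Accrual text).** Alpha 0.05, power 0.80, 25 methadone infants. Baseline/excessive rates: severe 8%/13%, oxygen or flow 13%/25%, tactile 8%/17%.

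**Step 1: reproduce the printed lists.** The upper SPRT limit is crossed when events ≥ h + s·n, where D = ln(p1/p0) + ln((1−p0)/(1−p1)), h = ln(0.80/0.05)/D = ln 16/D, and s = ln((1−p0)/(1−p1))/D.

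- Severe: D = 0.4855 + 0.0559 = 0.5414, h = 5.121, s = 0.1032. The 6th, 7th and 8th events stop if they come by infant 8.5, 18.2 and 27.9 (printed 8, 17, 27).
- Tactile: D = 0.7538 + 0.1029 = 0.8567, h = 3.236, s = 0.1202. The 4th to 7th events stop by 6.4, 14.7, 23.0 and 31.3 (printed 6, 14, 22, 30).
- Oxygen/flow: h = 3.456, s = 0.185. The 5th to 8th events stop by 8.4, 13.8, 19.2 and 24.6 (printed 8, 13, 18, 24).

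All printed values agree within one infant.

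**Step 2: compare the lists infant by infant**, read as running limits (an event count stops the trial if it is reached by the stated infant).

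| Infants | Severe limit | Tactile limit | Gap |
|---|---|---|---|
| 4–6 | 6 | 4 | 2 |
| 7–8 | 6 | 5 | 1 |
| 9–14 | 7 | 5 | 2 |
| 15–17 | 7 | 6 | 1 |
| 18–22 | 8 | 6 | 2 |
| 23–25 | 8 | 7 | 1 |

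If the lines marked as outside the sample do not bind, the severe list ends at infant 17 and the tactile list at infant 22. Infants 18–22 then have no severe limit at all.

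**Step 3: chance that a limit is reached within 25 infants**, by exact binomial recursion with all printed lines binding.

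| True rate | Severe list | Oxygen/flow list | Tactile list |
|---|---|---|---|
| 8% | 0.06% | 0.08% | 0.86% |
| 13% | 1.2% | 1.2% | 6.9% |
| 17% | 5.2% | 4.9% | 18.3% |
| 25% | 28.0% | 25.8% | 52.9% |

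With each category at its own excessive rate, the figures are severe 1.2%, oxygen/flow 25.8% and tactile 18.3%. By infant 13, severe against tactile is 0.06% v 2.1% at 13%, and 2.5% v 21.0% at 25%. Dropping the out-of-sample lines gives 0.4% v 6.5% at 13% and 10.7% v 49.9% at 25% within 25 infants.

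**Step 4: can 25 infants give 80% power for 8% v 13%?** Wald's expected sample at the excessive rate is (0.8·ln 16 + 0.2·ln(0.20/0.95)) / (p1·ln(p1/p0) + (1−p1)·ln((1−p1)/(1−p0))). For severe events this is 1.906/0.0145 ≈ 131 infants. For tactile it is about 45 and for oxygen/flow about 37. Even a single exact test after all 25 infants (reject at 5 or more, size 0.045) has 22% power at 13%.

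**Step 5: effect of using the item 3 counts for severe events.** Severe stopping takes the tactile column: 1.2% to 6.9% at 13%, and 28.0% to 52.9% at 25%. For any limit at baseline rates, treating the categories as independent: now 1 − 0.9994 × 0.9877 × 0.9914 = 2.1%; after, 1 − 0.9914 × 0.9877 × 0.9914 = 2.9%. Mutually exclusive categories give the same rounded figures; full overlap gives 1.7% both times. With all three at their excessive rates, stopping goes from 43/40/30% to 47/44/30% (exclusive/independent/full overlap).

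**The case against.** Several counter-arguments have weight.

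- **The lists follow from the stated rates.** A reader might infer a miscalculation. Step 1 rules that out: this is a consequence of the chosen rates. The source of the rates is not given, so their clinical merit cannot be judged here.
- **Severe is not looser than everything.** A reader might infer that the severe list is laxer than both moderate lists. With all printed lines binding it is level with the oxygen/flow list or one event above it through infant 24, and the two are reached about equally often at equal rates. The inversion is against the tactile list.
- **The trial is not unguarded below 6 severe events.** A reader might infer that nothing would happen. The documents do not support that: the monitor may stop on seriousness, reviews are scheduled after 13 and 25 infants whatever the count, the whole team monitors cardiorespiratory events, and unanticipated problems go to the IRB. Five severe events in 13 would be before the monitor at the first review. These safeguards stand, but they do not remove the inversion, because the section ties the meaning of unsafe to the printed thresholds. Removal for "Infant experiences an unexpected adverse event deemed related to study intervention" takes off only that infant.
- **The large gain is illustrative.** The plan uses 25% only for oxygen/flow. At the plan's own 13%, the changed list would still not be reached in about 93% of trials. The extreme patterns are also rare: five severe events in the first five infants has probability 0.004% at 13%.
- **The borrowed counts would no longer follow from 8% v 13%.** True, so the plan should give the reason for them openly.

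**Conclusion.** The point holds as a design weakness that is cheap to correct. From a shared 8% baseline, the severe list needs one or two more events than the tactile list at every infant from 4 to 25 with all printed lines binding. If the out-of-sample lines do not bind, the gap is one or two events for infants 4–17, and there is no severe limit for infants 18–22. The severe limit is reached in 1.2% of trials at its own excessive rate, so the cited 80% power is not delivered for that category. What is missing is a written severe trigger below 6 events and an immediate referral to the monitor between the scheduled reviews.

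The figures assume 25 methadone infants, running limits, independent infants with a constant event rate, and at most one counted event per infant in each category.

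**What to change.** Amend section 7.d as follows.

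1. Apply the item 3 counts to severe events: stop at 4 of the first 6, 5 of 14, 6 of 22 or 7 of 25. Keep 13% as the severe rate of concern.
2. Say that these counts are chosen so that severe events never face a looser limit than tactile ones.
3. State that the severe rule does not have 80% power at 13% with 25 infants.
4. Optionally, refer any death or life-threatening event to the existing monitor at once for a decision to stop or continue.

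The cost is a short amendment, with no new staff or data for the changed counts, and the small rise in stopping at baseline rates shown in step 5.
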